5.5.2 Sponsor Follow-Up

For serious adverse events, adverse events of special interest, and pregnancies, the Sponsor or a designee may follow up by telephone, fax, electronic mail, and/or a monitoring visit to obtain additional case details and outcome information (e.g., from hospital discharge summaries, consultant reports, autopsy reports) in order to perform an independent medical assessment of the reported case.

5.6 *ADVERSE EVENTS THAT OCCUR AFTER THE ADVERSE EVENT REPORTING PERIOD*

The Sponsor should be notified if the investigator becomes aware of any serious adverse event that occurs after the end of the adverse event reporting period (defined as the last study visit), if the event is believed to be related to prior study drug treatment.

The investigator should report these events directly to the Sponsor or its designee, either by faxing or by scanning and emailing the Serious Adverse Event/Adverse Event of Special Interest Reporting Form using the fax number or email address provided to investigators.

5.7 EXPEDITED REPORTING TO HEALTH AUTHORITIES, INVESTIGATORS, INSTITUTIONAL REVIEW BOARDS, AND ETHICS COMMITTEES

The Sponsor will promptly evaluate all serious adverse events and adverse events of special interest against cumulative product experience to identify and expeditiously communicate possible new safety findings to investigators, IRBs, ECs, and applicable health authorities based on applicable legislation.

To determine reporting requirements for adverse event cases, the Sponsor will assess the expectedness of these events using the following reference document:

- Lampalizumab Investigator's Brochure

The Sponsor will compare the severity of each event and the cumulative event frequency reported for the study with the severity and frequency reported in the applicable reference document.

Reporting requirements will also be based on the investigator's assessment of causality and seriousness, with allowance for upgrading by the Sponsor as needed.

6. STATISTICAL CONSIDERATIONS AND ANALYSIS PLAN

6.1 DETERMINATION OF SAMPLE SIZE

This study is open to all patients who complete study treatment and the Week 96 visit in parent Studies GX29176 and GX29185 and who meet the eligibility criteria (see Sections [4.1.1](#) and [4.1.2](#)).

6.2 SUMMARIES OF DEMOGRAPHIC AND BASELINE CHARACTERISTICS AND CONDUCT OF THE STUDY

Demographic and disease characteristics (such as GA area, BCVA, and VA under low-luminance conditions prior to enrollment) for patients enrolled in the extension study will be summarized *in all patients and* by treatment group in the parent study (Study GX29176 or Study GX29185). Patient disposition and exposure to study drug (number of study treatments and duration of treatment) will be summarized *in all patients and* by treatment group in the parent study.

6.3 SAFETY ANALYSES

The safety analyses will include patients enrolled in this study who receive at least 1 dose of study drug *in all patients and* according to treatment received in the parent study.

Verbatim descriptions of treatment-emergent adverse events will be coded, and their incidence will be summarized, as appropriate. Separate summaries will be generated for serious adverse events, deaths, adverse events leading to discontinuation of study drug, and adverse events judged to be related to lampalizumab. In addition, separate

summaries will be prepared for systemic (non-ocular) and ocular adverse events. Descriptive summaries will be generated for VA and IOP. All patients will receive lampalizumab treatment in this study; therefore, caution must be taken when interpreting safety results as there is no inactive/sham treatment group for comparison.

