3.2 END OF STUDY AND LENGTH OF STUDY

The end of the study is defined as the date when the last patient, last visit (LPLV) occurs.

The duration of the OLE study in each participating country will depend upon the health authority approval of lampalizumab in that country as well as the Sponsor's discretion. After completion of the Phase III OLE study, patients will have access to post-trial lampalizumab as outlined in the guidance in Section [4.3.4](#).

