4.6.2 Study Treatment Discontinuation

Patients must permanently discontinue study treatment if they experience any of the following:

- *Any medical condition that the investigator or Sponsor determines may jeopardize the patient's safety if he or she continues to receive study treatment*
- Pregnancy

The investigator has the right to discontinue a patient for reasons of non-compliance (e.g., missed doses and/or visits) or if the investigator or Sponsor determines it is in the best interest of the patient. The primary reason for the treatment discontinuation should be recorded on the appropriate eCRF.

Patients who must discontinue treatment will not be replaced or allowed to restart the study treatment. Any patient discontinued from study treatment will also be discontinued from the study and will not be allowed to re-enter the study; the patient will be encouraged to undergo a study early termination visit.

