4.6.3 Study and Site Discontinuation

The Sponsor has the right to terminate this study at any time. Reasons for terminating the study may include, but are not limited to, the following:

- The incidence or severity of adverse events in this or other studies indicates a potential health hazard to patients.
- Patient enrollment is unsatisfactory.
- Data recording is inaccurate or incomplete.

The Sponsor will notify the investigator if the Sponsor decides to discontinue the study.

The Sponsor has the right to close a site at any time. Reasons for closing a site may include, but are not limited to, the following:

- Excessively slow recruitment
- Poor protocol adherence
- Inaccurate or incomplete data recording
- Non-compliance with the ICH guideline for GCP
- No study activity (i.e., all patients have completed the study and all obligations have been fulfilled)

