5.3.1 Adverse Event Reporting Period

Investigators will seek information on adverse events at each patient contact. All adverse events, whether reported by the patient or noted by study personnel, will be recorded in the patient’s medical record and on the Adverse Event eCRF.

After completion of the Week 96 visit of the parent study and informed consent for the extension study has been obtained, any adverse events that are ongoing or started after the Week 96 visit of the parent study should be reported on the extension study Adverse Event eCRF.

All adverse events will be reported until *at least 30 days after the last dose of study drug or the last study visit, whichever is later*. After this period, the investigator should report any serious adverse events that are believed to be related to prior study drug treatment (see Section 5.6).

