Appendix 1 Schedule of Assessments (cont.)

Table 2 Study Flowchart for Q4W Arm: Week 56 through Week 96 and Early Termination (cont.)

- ^b This study may potentially extend beyond Week 96. *The sites will be informed in timely manner.*
- ^c To be administered by the site staff (except for the VA examiner) prior to any other visit assessments being performed on that day.
- ^d If laboratory sample is being obtained on study visit day, it must be obtain prior to fluorescein angiography (if applicable) and prior to study drug treatment.
- ^e Starting on Day 1, collect and perform the urine pregnancy test for women of childbearing potential, including those who have had tubal ligation, at each study drug treatment visit. If positive, collect the serum pregnancy sample and forward to central laboratory for testing, do not administer study drug, and if positive withdraw the patient from the study.
- ^f Optional aqueous sample will be collected from the patients who consented to it.
- ^g Perform prior to dilating the eyes.
- ^h Either MNRead charts or Radner Reading Charts will be performed during the study visit prior to dilating the eyes (see the tables in [Appendix 14](#) and [Appendix 15](#), respectively, for which chart to use according to country of the site). The test will be administered first monocularly (right/left eye) and then binocularly (both eyes).
- ⁱ To be performed post-dilation on the study eye only; the data will be forwarded to the central reading center.
- ^j Performed for both eyes; and results will be forwarded to the central reading center. See the center reading center manual. If a patient misses a study visit when ocular images are scheduled to be obtained, the images should be obtained at the next scheduled visit.

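### Section 6.3 summarizes the primary safety objective only as incidence, although length of follow-up varies by design; exposure-adjusted rates would be a cheap improvement

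*Combined protocol and SAP*

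**What the plan says.** Section 2.1 assesses the primary objective by the incidence and severity of ocular and of systemic (non-ocular) adverse events. For patients who receive at least one dose, Section 6.3 states: "Verbatim descriptions of treatment-emergent adverse events will be coded, and their incidence will be summarized, as appropriate". It adds separate tables for serious events, deaths, events leading to discontinuation, related events, and ocular and non-ocular events, overall and by parent-study treatment. It defines neither incidence nor treatment-emergent. Section 6.2 summarizes number of treatments and duration of treatment separately. A Data Analysis Plan is cited in Section 6.4, for anatomic and clinical outcomes; it is not among the documents.

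Follow-up has no common length:

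- Section 3.2: "The duration of the OLE study in each participating country will depend upon the health authority approval of lampalizumab in that country", and also on the Sponsor's discretion.
- Section 4.6.3: "The Sponsor has the right to terminate this study at any time".
- Section 4.6.2: "Any patient discontinued from study treatment will also be discontinued from the study and will not be allowed to re-enter the study".
- Appendix 1, Table 2, footnote b: "This study may potentially extend beyond Week 96".

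Two inputs to any rate need settling. Section 5.3.1 has events reported until "at least 30 days after the last dose of study drug or the last study visit, whichever is later", while Section 5.6 refers to "the end of the adverse event reporting period (defined as the last study visit". Section 5.3.1 also says that "any adverse events that are ongoing or started after the Week 96 visit of the parent study should be reported on the extension study" form, so events carried over from the parent study sit in the same dataset as new ones.

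**The concern.** A percentage of dosed patients answers a clear question only when patients are observed for similar times, or when the time is stated beside it. Here a low figure could mean low risk or short follow-up. The study has no concurrent control, as Section 6.3 itself warns, so readers will depend on absolute levels and on comparisons with other data. Unequal follow-up matters most for that use.

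The same holds for successive data cuts. Section 6.8 plans periodic interim safety analyses and Section 3.1.3 has the iDMC meeting about every 6 months. A crude percentage tends to rise from one cut to the next as follow-up accumulates, even at constant risk.

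**Working it through.** The plan contains no figure to reproduce: 1800 is an enrolment cap, and Section 6.1 gives no event rate or precision target. The check is therefore illustrative. **Assumed:** constant first-event rates r of 0.05, 0.10 and 0.30 per patient-year, and a 48-week country closure. **From the documents:** flowcharts to Week 96, possible extension beyond it, the 30-day tail in Section 5.3.1, and Q4W or Q6W dosing.

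**1. Crude incidence by length of follow-up.** Incidence = 1 − exp(−r × (7 × weeks + 30)/365.25). At 48 weeks the time is 366/365.25 = 1.002 years; at 96 weeks it is 702/365.25 = 1.922 years.

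| r | 24 wk | 48 wk | 96 wk | 144 wk |
|---|---|---|---|---|
| 0.05 | 2.7% | 4.9% | 9.2% | 13.2% |
| 0.10 | 5.3% | 9.5% | 17.5% | 24.7% |
| 0.30 | 15.0% | 26.0% | 43.8% | 57.4% |

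The underlying rate is constant along each row.

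**2. Country mix.** If half the patients are in countries closing at 48 weeks and half at 96, pooled incidence is (4.9 + 9.2)/2 ≈ 7.0% at r = 0.05 and (26.0 + 43.8)/2 = 34.9% at r = 0.30.

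**3. Successive cuts at r = 0.30.** If all patients entered together, 1 − exp(−0.30t) at 0.5, 1, 1.5 and 2 years gives 13.9%, 25.9%, 36.2% and 45.1%. Entry is in fact staggered, because each patient joins at his or her own parent-study Week 96 visit (Section 3.1.1). With uniform entry over an assumed two years, 1 − (1 − exp(−0.30t))/(0.30t) gives 7.1%, 13.6%, 19.5% and 24.8%. The level differs; the rise remains.

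**4. Does the Section 6.2 exposure table suffice?** Take duration as first to last dose (an assumption): 672/365.25 = 1.840 years at 96 weeks. Dividing first-event patients by it gives, per 100 patient-years:

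- r = 0.05: 0.0916/1.840 = 5.0, against 5
- r = 0.10: 0.175/1.840 = 9.5, against 10
- r = 0.30: 0.438/1.840 = 23.8, against 30, about 21% low

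The shortfall arises because total duration includes time after a patient's first event.

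**5. Regimen contrast.** Scheduled injections through Week 96 are 1 + 96/4 = 25 (Q4W) and 1 + 96/6 = 17 (Q6W); through Week 48 they are 13 and 9. With per-injection risk p, incidence is 1 − (1 − p)^n. For p = 0.1%, 0.5% and 1% (assumed), the Q4W/Q6W ratio is 1.465, 1.442 and 1.415 at 96 weeks. With half of each arm closing at 48 weeks it is 1.457, 1.438 and 1.415. Variable duration barely moves it.

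**6. End of adverse event reporting.** Read Section 5.3.1 as the later of 30 days after the last dose and the last visit. An early termination visit falls at least 30 days after the last treatment (Section 4.6), so for anyone who attends one, Sections 5.3.1 and 5.6 give the same date. They differ only when the last visit is less than 30 days after the last dose, for example when it is a treatment visit. If that applied to every patient, dropping the 30 days at r = 0.30 would give 24.1% rather than 26.0% at 48 weeks and 42.4% rather than 43.8% at 96 weeks. That is an upper bound at this rate; at r = 0.05 the differences are about 0.4 points (4.5% against 4.9%; 8.8% against 9.2%).

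**The case against.** The study is descriptive, with no test, error rate or margin to distort. A percentage of dosed patients beside an exposure table is a legitimate summary, Section 6.3 already urges caution, and step 4 shows that the exposure table nearly suffices for rare events. The wording of Section 6.3 leaves room for rates, and the unseen Data Analysis Plan or iDMC charter may contain them. Every magnitude here rests on assumed rates. All of this stands, and it is why the point is an improvement and not an error. It does not remove the point: the exposure table is not tied to event counts and does not recover the rate of common events.

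Four stronger readings are tempting, and the documents do not support them:

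- **No exposure-adjusted analysis will be done.** The text shows only that none is specified here.
- **The comparison of dosing regimens is biased by unequal follow-up.** Step 5 shows almost no effect.
- **Follow-up of all events stops when treatment stops.** Section 4.6.1 asks sites to make every effort to keep following serious events, deaths and events of special interest after discontinuation unless consent is withdrawn.
- **Sections 5.3.1 and 5.6 conflict for every patient.** Step 6 shows that they diverge only in a limited case.

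**Conclusion.** The point holds as a recommended, low-cost improvement. As specified, the pooled crude percentage and its level at each data cut mix risk with length of follow-up. Under constant hazards, follow-up of 96 rather than 48 weeks raises it from 4.9% to 9.2% at 0.05 per patient-year and from 26.0% to 43.8% at 0.30, with no change in risk. These sizes depend on the assumed rates, the assumed 48-week closure and the 30-day tail. That time at risk varies by design rests on the documents alone. No hypothesis test is affected, and the regimen contrast changes little.

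**What to change.** In Section 6.3, keep the incidence table, state that it is a percentage of dosed patients, and add two measures, each overall and by parent-study treatment group:

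1. Patients with a first treatment-emergent event per 100 patient-years at risk, with time counted from the first extension dose to the first event or the end of adverse event reporting, and exact Poisson 95% confidence intervals.
2. Study-eye ocular events per 1,000 injections, with a confidence interval that allows for clustering within patients. Patient-year rates do not remove the planned 25 to 17 difference in injections; this measure does.

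Define treatment-emergent so that an event already ongoing at the first extension dose is not counted as new unless it worsens. Reconcile the end of adverse event reporting in Sections 5.3.1 and 5.6, and use that one end for numerator and denominator.

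The cost is one paragraph and a few tables, since event start dates and numbers of treatments are already collected. Three limits should be stated: there is more output; a patient-year rate is easy to interpret only if the hazard is roughly constant; and neither measure corrects for informative censoring. The last concerns mainly non-serious events, because serious events, deaths and events of special interest are to be followed after discontinuation unless consent is withdrawn.

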6.4 ANATOMIC AND CLINICAL OUTCOME ANALYSES

The anatomic and clinical outcome analyses will include *all* patients enrolled in this study who *have received at least one dose of study drug. The analyses will be summarized in all patients and by treatment group in the parent study.*

Descriptive summaries will be generated for all anatomic and clinical outcomes, including PROs, over time. Correlation between anatomic and clinical outcomes will be summarized. Additional details of analysis will be included in the Data Analysis Plan.

6.5 PHARMACOKINETIC ANALYSES

The PK analyses will include all enrolled patients who have *received at least one dose of study drug and have at least one serum sample. The analyses will be summarized by treatment group in the parent study.* Serum concentrations of lampalizumab will be summarized descriptively.

Concentrations of lampalizumab from the optional collection of aqueous humor may be reported and/or summarized as appropriate. Additional PK/PD and exposure–response analyses may be conducted as appropriate. Population PK modeling may be performed to characterize inter-individual variability, which may be reported separately from the Clinical Study Report.

6.6 IMMUNOGENICITY ANALYSES

The immunogenicity analyses will include patients with at least one predose (*defined as prior to the first dose in the extension study for the prior sham patients, and prior to the first dose in the parent study for the prior lampalizumab patients*) and one postdose ATA assessment. *The analysis will be summarized by treatment group in the parent study.*

The number and proportion of ATA-positive and ATA-negative patients during this study will be summarized by treatment group. The relationship between ATA status and the safety, efficacy, PK, and biomarker endpoints will be analyzed and reported descriptively in subgroup analyses. Patients are considered to be ATA--positive if they are ATA-negative at baseline (*defined as the last measurement prior to the first dose in the extension study for the prior sham patients, and the last measurement prior to the first dose in the Parent study for the prior lampalizumab patients*) but develop an ATA response following study drug administration (i.e., treatment-induced ATA response) or if they are ATA-positive at baseline and the titer of one or more post-baseline samples is at least 4-fold greater (i.e., ≥ 0.60 titer units) than the titer of the baseline sample (i.e.,

treatment-enhanced ATA response). Patients are considered to be ATA-negative if they are ATA-negative at baseline and all post-baseline samples are negative or if they are ATA-positive at baseline but do not have any post-baseline samples with a titer that is at least 4-fold greater than the titer of the baseline sample (i.e., treatment unaffected).

The relationship between ATA status and the safety, efficacy, PK, and biomarker endpoints will be analyzed and reported descriptively via subgroup analyses.

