2.4 IMMUNOGENICITY OBJECTIVES

The immunogenicity objective for this study is to evaluate the immune response to lampalizumab through the analysis of the incidence of anti-therapeutic antibodies (ATAs) during the study relative to the prevalence of ATAs at baseline.

The exploratory immunogenicity objective for this study is to evaluate potential effects of ATAs on the efficacy, safety, biomarker, or PK endpoints.

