Appendix 1 Schedule of Assessments

Table 1 Study Flowchart for Q4W Arm: Day 1, Week 4 through Week 52, and Early Termination

Assessment Window (Days)	Day 1 ^a		Week													ET ^b
	Data Extracted from Parent Study	Data Obtained at Day 1 Visit	4	8	12	16	20	24	28	32	36	40	44	48	52	≥30
			±5	±5	±5	±5	±5	±5	±5	±5	±5	±5	±5	±5	±5	
Written informed consent		x ^c														
Review of inclusion and exclusion criteria		x														
Demographic information (age, sex, and self-reported race/ethnicity) ^d	x															
NEI VFQ-25 ^e (as applicable)	x							x						x		x
FRI Index ^e (as applicable)	x							x						x		x
Vital signs ^f																x
Central laboratory samples (hematology, coagulation, chemistry panel, and urinalysis) ^g																x
Biomarker plasma sample ^g		x														
Urine pregnancy test ^{g,h}		x	x	x	x	x	x	x	x	x	x	x	x	x	x	
Serum ATA sample ^g	x													x		x

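### ATA status comes from any post-baseline sample and carries no timing rule, so the safety and efficacy subgroup tables cannot show whether antibody preceded outcome in patients first found positive in the extension

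*Combined protocol and SAP*

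**What the plan says.** Section 6.6 assigns ATA status once per patient. A patient negative at baseline becomes positive on any sample showing that they "develop an ATA response following study drug administration". A patient positive at baseline becomes treatment-enhanced if the "titer of one or more post-baseline samples is at least 4-fold greater" than at baseline. The negative label requires a patient to be "ATA-negative at baseline and all post-baseline samples are negative", or positive at baseline with no qualifying rise. Baseline is before the first extension dose for prior-sham patients and before the first parent-study dose for prior-lampalizumab patients.

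The same section then uses this label as a subgroup factor and says so twice, the first time as: "The relationship between ATA status and the safety, efficacy, PK, and biomarker endpoints will be analyzed and reported descriptively in subgroup analyses". Section 2.4 gives the purpose, as an exploratory objective: to "evaluate potential effects of ATAs on the efficacy, safety, biomarker, or PK endpoints". The main immunogenicity objective there is ATA incidence relative to baseline prevalence.

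In Appendix 1 the row "Serum ATA sample" is marked at Day 1 (extracted from the parent study), Week 48, Week 96 and early termination, for both Q4W and Q6W. Appendix 2 lists no ATA sample at an unscheduled safety visit. Adverse events are collected throughout the extension (Section 5.3.1), and the primary endpoints in Section 2.1 are incidence and severity with no sub-period.

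**The concern.** An effect of ATA on an outcome requires the antibody to come first. A label that is settled only when the last sample is in cannot show that order. Take a prior-sham patient with intraocular inflammation at Week 8 who is negative at Week 48 and first positive at Week 96. The subgroup table counts this as inflammation in an ATA-positive patient.

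Follow-up length adds a second difficulty. Patients who stay longer give more samples and have more time to convert, and they also have more time for an adverse event. This can produce an association even if ATA does nothing.

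The stakes are interpretive. A reader could take such a table as evidence that ATA drives inflammation or loss of effect, or that it does not. Section 6.8 allows exploratory analyses of interim data to support regulatory submissions, so the table may be read outside the study team.

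**Working it through.** The plan states no figure on this point, so there is none to reproduce. The check sets the labelling rule against the sampling schedule, then asks how large a spurious association could be.

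**Who is affected.** Patients first found positive in the extension: every prior-sham patient who tests positive, and prior-lampalizumab patients who convert after the parent study. Prior-lampalizumab patients already positive at parent Week 96 have all their extension events after detection.

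**Injections before the first scheduled post-dose ATA result (prior-sham patients, Appendix 1).**
- Q4W: Day 1 plus Weeks 4 to 44 = 1 + 11 = 12, out of 1 + 24 = 25 through Week 96.
- Q6W: Day 1 plus Weeks 6 to 42 = 1 + 7 = 8, out of 1 + 16 = 17.

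**Share of Day 1 to Week 96 time before detection, in converters who stay on study.** Detection at Week 48 gives 48/96 = 50%; at Week 96 it gives 96/96 = 100%. If a fraction f is first detected at Week 48, the share is 0.5f + 1.0(1 − f):
- f = 0.75: 62.5%
- f = 0.50: 75%
- f = 0.25: 87.5%

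With a constant event rate, the same share of these patients' events precedes detection.

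**Patients withdrawn early.** Table 1 in Section 5.1.2 withdraws patients with more than 3+ intraocular inflammation or study-eye endophthalmitis. The early termination sample is taken at least 30 days after the last dose. A prior-sham patient withdrawn this way before Week 48 can be labelled only by a sample taken after the event. Without that sample there is no scheduled post-dose result, and the patient falls outside the Section 6.6 population.

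**Size of a spurious association.** This was simulated with no ATA effect and 1,000,000 patients per scenario, all negative on Day 1. None of these inputs comes from the documents:
- independent, constant hazards for first event, conversion and dropout;
- 20% event risk over 96 weeks;
- 5%, 15% or 30% conversion over 96 weeks;
- 0%, 20% or 40% dropout over 96 weeks;
- early termination samples from 0%, 50% or 100% of dropouts, taken 30 days after dropout.

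Patients with no post-dose sample are excluded, as Section 6.6 requires. Crude ATA-positive to ATA-negative incidence ratio (range over the three conversion rates):

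| Dropout | No early termination samples | Half of dropouts sampled | All dropouts sampled |
|---|---|---|---|
| 0% | 0.99–1.00 | 0.99–1.00 | 0.99–1.00 |
| 20% | 1.01 | 1.05–1.06 | 1.07–1.10 |
| 40% | 1.02–1.03 | 1.10–1.13 | 1.19–1.22 |

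For example, with 15% conversion, 40% dropout and all dropouts sampled, incidence is 18.4% in ATA-positive and 15.5% in ATA-negative patients, a ratio of 1.19. Across all scenarios, 74% to 77% of first events in ATA-positive patients came before detection, and 48% to 51% before true conversion.

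**The case against.** The strongest reply is that this is an exploratory, descriptive analysis. No test, error rate or primary conclusion depends on it, and ever-positive status is the natural definition for the main objective, ATA incidence. That stands. It limits the consequence, but it does not make the subgroup table informative about order.

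A reader might infer that the plan prescribes comparing outcomes over the whole study. It does not say so; that reading follows from the absence of any window in Section 6.6 and the undivided adverse event endpoint. Section 6.4 defers further detail to a Data Analysis Plan that is not among the documents. That plan might set a window for clinical outcomes, but Section 6.6 does not refer to it.

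A reader might also infer that events before detection came before the antibody. Detection is not onset. A Week 48 positive converted at some unknown earlier time, so a Week 8 event may lie on either side. That is why 74% to 77% before detection falls to about half before conversion, and even that rests on an assumed constant conversion hazard.

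A third tempting reading is that about half of all prior-sham patients' adverse events are misplaced. The documents do not support it. A patient negative at every sample has no later positive to reverse the order; only converters are affected, and their number is not given.

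Finally, a Week 48 landmark alone would be a poor replacement. It drops every earlier prior-sham event from the comparison and excludes patients withdrawn before Week 48, including those withdrawn for severe inflammation. This objection stands, and it shapes the fix.

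**Conclusion.** The point holds for patients first found positive in the extension. For them, outcomes before the first positive sample are counted as ATA-positive outcomes, and the planned table cannot address the exploratory objective of ATA effects. The main harm is lost temporal order.

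The added bias from unequal follow-up looks modest: none without dropout, and about 1.2 in the most extreme scenario tried. That figure rests wholly on assumed event, conversion, dropout and sampling rates. The true size is unknown. It would be wrong to conclude that the planned table must exaggerate ATA harm, or that the primary safety evaluation is compromised.

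PK is less exposed, because serum PK and ATA samples share visits. Even so, a first positive at Week 96 would also relabel that patient's Week 48 concentration. The text also leaves open whether a positive sample from the parent study alone counts as positive during the extension; this should be stated.

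**What to change.** In Section 6.6:
- Keep ever-positive status for ATA incidence.
- For prior-lampalizumab patients, relate ATA status on Day 1 (parent Week 96) to extension adverse events, BCVA and GA change.
- For prior-sham patients, add a landmark analysis of Week 48 status against later outcomes, labelled as restricted to patients still on study at Week 48. It supplements the planned table and does not replace it.
- Keep all earlier prior-sham events and early-terminated patients in the report. List the date of the last negative and first positive sample beside each event onset, so that uncertainty about onset is visible.
- Split events in ATA-positive patients into before and after first detection.

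No new samples are needed. The cost is wording and some extra programming. The prior-sham landmark comparison is shorter and selects patients who remained on study, and late converters count as negative in the Day 1 analysis. Both limits should be stated with the results.
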